6.2 Secondary Endpoints

Secondary endpoints will include the following:

- Quantify injury associated with different baseball movement using the proposed system.
- Development of algorithms to quantify workloads associated with injury during common baseball movements.
- Validation of basic device measurements (Pilot Phase)

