2.2 Secondary Objectives (or Aim)

The secondary objectives are to:

- Develop algorithms to quantify injury associated with common baseball injuries
- Evaluate the feasibility of wearing the throwing monitor during a simulated baseball game

- Validate simplistic device measurements (Pilot Phase)

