3.2 Study Duration, Enrollment and Number of Sites

3.2.1 Duration of Study Participation

The study duration per subject will be 1 day for screening, and 1 day for throwing evaluation for both the Pilot and Phase 1 groups.

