4.3 Subject Completion/Withdrawal

Subjects may withdraw from the study at any time without prejudice to their care (if applicable). They may also be discontinued from the study at the discretion of the Investigator for lack of adherence to study protocols (i.e. wearing the device at appropriate times), failure to follow visit schedules, injury that prevents the subject from throwing or participating in the study, or any AEs. The Investigator may also withdraw subjects who violate the study plan, or to protect the subject for reasons of safety or for administrative reasons. It will be documented whether or not each subject completes the clinical study. If the Investigator becomes aware of any serious, related adverse events after the subject completes or withdraws from the study, they will be recorded in the source documents and on the CRF.

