5 STUDY EVALUATIONS AND MEASUREMENTS

5.1 Screening and Monitoring Evaluations and Measurements

5.1.1 Medical Record Review

Patients enrolled in the Pilot Phase will undergo limited electronic medical record review of the following variables:

- Date of birth
- Height and weight
- Demographics including sex and race
- Primary diagnosis
- Prescribed physical therapy
- Medical history of current and previous injuries

Patients enrolled in Phase 1 will not necessarily be CHOP patients and thus will not undergo medical record review, but will instead be given a brief demographic survey.

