Movement Phase Segmentation: After detection and classification, movements are further segmented into constituent phases. The true phase of the movement is modeled as a hidden Markov model where time series data or windowed feature data derived from the time series data are used as emissions of the Markov process. Using the set of emissions recorded, the optimal set of series of states is calculated using the Viterbi algorithm [2]. Emissions distributions for the phases of a movement are determined from truth data gathered in the Epic Sports Biomechanics research facility.

Biomechanical interpretations: Pseudo Biomechanical Variables (PBVs) related to the true biomechanical values such as torques on joints and forces applied to ligaments are estimated at the final stage in the processing pipeline. This is accomplished using a combination regression analysis and a phase-specific simplified inverse biomechanical model. Since movement phases are associated with specific biomechanical configuration and displacements of the body segments within a phase are constrained by design, the inverse mapping is determined over a smaller problem subspace. Regression analysis is used offline to calculate a mapping between biomechanical values of interest (e.g. torque in shoulder) and sensor measurements (e.g. x dimension acceleration). The regression is simplified through use of the least absolute shrinkage and selection operator (LASSO) to determine the

minimum set of active joint variables to improve computational performance when executed on sensor hardware in real-time [42].

These values are then used to determine the probability of injury as well as calculate performance estimates such as pitch velocity. PBVs are also paired with movement phase information, stored, and available for viewing by the player, parents, and coaches to aid in quick identification of problems with form or opportunities to improve performance. Injury estimation cost functions will score actions based on the potential for accumulated overuse injury risk. For example, large forces on the UCL during the stride phase of a baseball pitch due to an excessive rotation of the forearm from the horizon to the vertical plane would accumulate a higher cost than a similar pitch with proper form [43].

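### The first secondary endpoint and the injury probability in 5.2.1 cannot be estimated as injury, or validated against it, here; the study can deliver a load-based score

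*Combined protocol and SAP*

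**What the plan says.** **What is promised.** The first secondary endpoint in section 6.2 is "Quantify injury associated with different baseball movement using the proposed system". The second is "Development of algorithms to quantify workloads associated with injury during common baseball movements", which corresponds to the section 2.2 objective "Develop algorithms to quantify injury associated with common baseball injuries". Section 5.2.1 takes the estimated joint torques and ligament forces (the Pseudo Biomechanical Variables) and says: "These values are then used to determine the probability of injury as well as calculate performance estimates such as pitch velocity". It adds: "Injury estimation cost functions will score actions based on the potential for accumulated overuse injury risk".

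**What is provided.** Section 3.2.1 limits participation to "1 day for screening, and 1 day for throwing evaluation", in both phases. After that, section 4.3 provides for recording only in this case: "If the Investigator becomes aware of any serious, related adverse events after the subject completes or withdraws from the study". Injury history is gathered. The Pilot Phase record review includes "Medical history of current and previous injuries" (5.1.1) and imaging (5.1.3). Both phases have an interview on current and past injury (5.1.2) and an athletic history survey (5.1.4). Section 6.3 assigns none of this to an analysis.

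**The concern.** An endpoint needs an outcome, an analysis that uses it, and a way to judge the answer. If the first 6.2 bullet means injury, it has none of the three. The same holds for the probability in 5.2.1: a probability of injury must be calibrated against injuries that occur, and none are to be observed for that purpose.

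Two things are at stake. The final report could not answer the first secondary endpoint in its plain sense. And a score built from loads could be read as an injury result. Section 5.2.1 foresees the device values being shown to players, parents and coaches, and the sentence on probability carries no caveat.

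**Working it through.** **1. The plan's own figures.** Section 6.4 enrols 20 per phase to obtain 10 evaluable. Then 2 × 20 = 40 enrolled and 2 × 10 = 20 evaluable, which agrees with section 3.2.2. No injury rate, event count or precision target is given, so there is no injury figure to reproduce. The rest of the check is structural.

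**2. Is there an injury outcome after the measured throws?**

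| Source | Phase | Timing and use |
|---|---|---|
| Survey (5.1.4) | both | retrospective; no analysis assigned |
| Interview (5.1.2) | both | current and past; no analysis assigned |
| Medical record, imaging (5.1.1, 5.1.3) | Pilot | current and past; no analysis assigned |
| Adverse events (7.1) | both | safety monitoring during the study; not an endpoint |
| Serious, related events after completion (4.3) | both | only if the investigator happens to learn of them |

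Scheduled days after the throwing day: 0, in all 20 evaluable subjects. Current injury does not fill the gap. The Pilot Phase excludes throwing-arm injury, and Phase 1 excludes injury that impedes baseball movements (3.3.2).

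**3. Does any planned analysis use an injury variable?** Section 6.3.1 names four quantities.

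| Quantity | What it is judged on | Injury used? |
|---|---|---|
| Movement detection | sensitivity and specificity | no |
| Movement classification | sensitivity and specificity | no |
| Phase segmentation | phases marked by the biomechanist from video (6.3.2) | no |
| Sensor-to-biomechanics mapping | motion-capture values | no |

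Count: 0 of 4. Section 6.3.2 mentions overuse injury only to say which movements are of interest; its outputs are torques, forces, phases and flags for poor form.

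**4. Which link is tested?** The chain in 5.2.1 has three links:

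- sensor signal → estimated load
- estimated load → score, through the cost functions
- score → injury

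Section 6.3.1 tests the first: mean error below 5% and standard deviation below 10% of the nominal value, against motion capture. The second depends on weights for which 5.2.1 gives no source beyond one cited example about elbow ligament load. The third requires comparing the score with injuries observed, and step 2 shows that none are collected for this. Meeting the 6.3.1 criterion would therefore validate load and leave the injury probability untested.

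**5. Text affected.** Secondary endpoints in 6.2: 3. Affected in its injury reading: 1 (the first). Affected only in the link to injury: 1 endpoint (the second) and 1 objective (in 2.2). The third endpoint, validation of basic device measurements, is untouched.

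**The case against.** The best defence reads the first endpoint through its closing reference to the proposed system. On that reading it is the output of the 5.2.1 cost functions: a score per movement, built from estimated loads. Phase 1 supplies the data for that score, and 6.3.1 checks its load inputs. **This stands.** A reader might infer that the endpoint has no data at all or could not be reported; the documents do not support that. What is missing is a definition of the score and any basis for calling it injury or a probability of injury.

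Second, the study calls itself exploratory (6.4) and sets feasibility as the goal of analysis (6.3.1). Parts of 5.2.1 also describe the future product, down to a tennis example. This lowers the risk of misreading. But the exploratory label in 6.4 explains the absence of a power calculation, and the sentence promising a probability has no such label.

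Third, injury history is collected, and Phase 1 does not exclude healed injuries, so a descriptive table of load by past injury is possible. It would be wrong to say the study has no injury data. Those data precede the measured throws, however, and no analysis of them is planned.

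**Conclusion.** The concern holds in this form: the first 6.2 endpoint and the 5.2.1 probability cannot be estimated as injury or validated against injury in this study. The grounds are 0 scheduled follow-up days in 20 evaluable subjects, no prospective injury outcome, and 0 of 4 planned quantities involving injury. The deliverable is a load-based device score with load inputs checked against motion capture, available for the 10 evaluable Phase 1 subjects.

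A reader might go further and conclude that the 2.2 algorithm objective and the second endpoint also fail. They do not: both can be met as algorithm development for workload, and only their link to injury is out of reach. Nor are the primary endpoint (6.1) or the 6.3.1 success criteria affected.

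The conclusion assumes no numerical injury rate. It rests on the documents containing no injury outcome or injury analysis other than those listed above. The change should be made, because it alters what the study may conclude.

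**What to change.** Change the wording only:

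- **6.2, first bullet:** *Describe the device-derived load-based score, and the joint, ligament and muscle loads behind it, by movement type in Phase 1, using the proposed system.*
- **6.2, second bullet, and the matching 2.2 objective:** *Develop algorithms to quantify workload during common baseball movements.* This keeps the algorithm objective and keeps the two sections aligned.
- **5.2.1:** in place of the probability of injury, write *an exploratory load-based score, not validated against injury in this study*, and state the source of any injury weighting in the cost functions.
- **6.3, add:** *No conclusion on injury risk or probability will be drawn from this study; any summary of load by past injury is descriptive only.*

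No visits, subjects or measurements are added. The cost is a narrower claim, plus the work of defining the score and documenting its weights. Keeping the device in the first bullet distinguishes it from the primary endpoint, which concerns motion-capture data.

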6.3 Statistical Methods

6.3.1 Baseline Data

Data will be analyzed with the goal of determining the feasibility of the approach. The accuracy of movement classification, movement phase segmentation, mapping of sensor reading to biomechanical values, and movement detection will all be quantified. K-fold cross validation will be used to estimate the performance of regressors and classifiers. Regressor performance will be quantified via the mean and standard deviation of error values between predicted biomechanical variable values and actual values as determined from motion capture data. Biomechanical value prediction models will be considered successful if error distributions have mean and standard deviation of less than 5% and 10% respectively of the nominal value. Sensitivity and specificity will be used to quantify the

performance of movement detection and classification algorithms. Movement segment detection will be considered correct if the algorithm identifies 90% of time occupied by the movement. Detection algorithms will be considered successful if they are able to operate with specificity and sensitivity of 95%.

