1 BACKGROUND INFORMATION AND RATIONALE

1.1 Introduction

Overuse injuries in youth athletes are commonplace. Current methods of prevention and progressive loading during rehabilitation are rudimentary (e.g. baseball pitch count) and fail to account for the subtleties of differing player technique or effort. A system capable of quantifying biomechanical loads associated with sports movements would substantially aid physicians, therapists, guardians, and coaches in prevention and rehabilitation efforts.

Study team partners at Innovative Design Labs (IDL) in collaboration with Reality Works Inc. have developed a prototype for an advanced wearable device that has potential to track cumulative exposure to injurious forces, monitor adherence to sport-specific overuse standards and rehab regimens, and identify improper throwing technique. The purpose of this study is to collect preliminary and advanced motion data from youth athletes in order to create and refine an algorithm to quantify throwing movements, numbers, and injury associations among youth baseball players for use in this wearable throwing monitor. The Pilot Phase of the study will occur in the CHOP rehabilitation clinic while wearing the prototype device and aims to test and refine rudimentary throwing algorithms using simple throwing and movement tasks. Phase 1 of the study will occur at the Epic Sports Biomechanics research facility and will collect advanced motion-capture data during simulated baseball play in order to improve system hardware, firmware, and algorithms.

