8.5 Recruitment Strategy

Participants for the Pilot Phase will be recruited from orthopaedics physical therapy clinics at CHOP. Potential subjects will be identified by a member of the study team based on screening sports medicine physical therapy clinic schedules against the inclusion/exclusion criteria. Patients who are qualified for the study (based on the inclusion/exclusion criteria) will be approached and consented during their physical therapy visit.

Participants for Phase 1 will be recruited from multiple sources including solicitation letters sent to local youth sport organizations, fliers placed in the Sports Medicine Centers throughout CHOP organization, and or personal solicitation via email, phone, or in-person contact. Patients who are qualified for the study (based on inclusion/exclusion criteria) and who respond to solicitation or other recruitment strategies will be consented via e-consent processes using REDCap and will have the opportunity to ask questions during a phone call with a member of the study team prior to signing the eConsent. At the biomechanics laboratory for throwing performance housed at Epics Sports Biomechanics, the subjects will undergo additional data collection within the 3-D motion laboratory in order to augment training data and re-estimate the accuracy of the various algorithmic components.

For the Pilot Phase, a convenience sample of 20 youth athletes will be recruited to participate. Recruitment will stop when 10 evaluable subjects have undergone data collection.

For Phase 1, a convenience sample of 20 youth baseball pitchers, will be recruited to participate in this study. Recruitment will stop when 10 evaluable subjects have undergone data collection.

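### Section 6.3.1 scores the algorithm chain by component only, so meeting its two success marks does not bound the error in session workload

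*Combined protocol and SAP*

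**What the plan says.** Section 5.2.1 describes a serial chain. Sensor data are filtered, movements are separated and classified, each movement is divided into phases, and phase-specific load variables "are estimated at the final stage in the processing pipeline". Each step works on the output of the step before.

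Section 6.3.1 sets out how performance is measured: "The accuracy of movement classification, movement phase segmentation, mapping of sensor reading to biomechanical values, and movement detection will all be quantified". It treats the four components as follows.

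- **Detection** has a success mark: "Detection algorithms will be considered successful if they are able to operate with specificity and sensitivity of 95" percent.
- **Biomechanical prediction** has a success mark: "Biomechanical value prediction models will be considered successful if error distributions have mean and standard deviation of less than 5% and 10% respectively". Both percentages are relative to a nominal value. The sign of the mean error is not restricted.
- **Classification** has a measure but no mark. Sensitivity and specificity describe the "performance of movement detection and classification algorithms", while the 95% sentence names detection alone.
- **Phase segmentation** has no mark. The sentence "Movement segment detection will be considered correct if the algorithm identifies 90% of time occupied by the movement" defines when one movement segment counts as correct. It does not say what proportion must be correct.

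Section 8.5 keeps to the same level and speaks of using the Phase 1 data to "re-estimate the accuracy of the various algorithmic components".

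Workload is nevertheless an intended output. Section 1.1 says the device has the potential to "track cumulative exposure to injurious forces", Section 5.2.1 scores actions for accumulated injury risk, and Section 6.2 has a secondary endpoint on quantifying workload. The nearest thing to a test of the whole device is in Section 3.1.2, where the Pilot Phase is to show whether the pitch count is accurate. No threshold, reference method or load comparison is given there.

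**The concern.** In a serial chain, good components do not guarantee a good final output. A throw that is never detected contributes nothing to the session's load. A throw given the wrong class or wrong phases is passed to the wrong phase-specific mapping. A bat swing taken for a throw adds load that did not occur. None of these errors need appear in the regression error, which compares predicted with actual values and has no stated rule for throws without a prediction.

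The plan could therefore be followed exactly, both success marks met and the approach called feasible, while the session workload is materially wrong in either direction. Nothing planned would reveal it.

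**Working it through.** The documents give no end-to-end figure, so there is none to reproduce. The question is what error in session load is compatible with meeting the two stated marks.

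**Inputs from Section 6.3.1**

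- Detection sensitivity 0.95 and specificity 0.95, the latter allowing 5% of non-throws to be accepted.
- Mean regression error up to 5% in either direction, so a factor b between 0.95 and 1.05. The mark is strictly below 5%, so these are limiting values.

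**Assumptions not in the documents**

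- Classification is 95% correct (used in the right-hand column only).
- R = non-throw movements per true throw, and w = load credited to a false detection relative to a true throw. Several values are shown.
- Stage errors are independent of each other and of the size of the load.

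**Formula**

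Load ratio = b x (s + 0.05 x R x w), where s is the share of true throws that reach the load stage. With detection only, s = 0.95. With detection and classification, s = 0.95 x 0.95 = 0.9025. The error is the ratio minus 1.

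| Bias factor b | False detections | Detection only | With classification at 95% (assumed) |
|---|---|---|---|
| 0.95 | none | 0.95 x 0.95 = 0.9025 (-9.75%) | 0.95 x 0.9025 = 0.857 (-14.3%) |
| 1.00 | none | 0.95 (-5.0%) | 0.9025 (-9.75%) |
| 1.05 | none | 1.05 x 0.95 = 0.9975 (-0.25%) | 1.05 x 0.9025 = 0.948 (-5.2%) |
| 0.95 | R = 1, w = 0.5 | 0.95 x 0.975 = 0.926 (-7.4%) | 0.95 x 0.9275 = 0.881 (-11.9%) |
| 0.95 | R = 2, w = 1 | 0.95 x 1.05 = 0.9975 (-0.25%) | 0.95 x 1.0025 = 0.952 (-4.8%) |
| 1.05 | R = 3, w = 1 | 1.05 x 1.10 = 1.155 (+15.5%) | 1.05 x 1.0525 = 1.105 (+10.5%) |

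**Scale.** For the 30 to 45 pitches of a Phase 1 simulated game (Section 4.2.2), the first cell means load equivalent to 30 x 0.9025 = 27.1 or 45 x 0.9025 = 40.6 pitches.

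**Role of the SD mark.** If pitch-level errors are independent, an SD of 10% averages down over a session to 10%/√30 = 1.8% or 10%/√45 = 1.5%. The session total is therefore governed mainly by missed throws, false detections and mean bias. The SD mark does not limit these.

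**The case against.** The strongest defence is the stage of the work. Section 6.4 calls the study exploratory, the primary endpoint in Section 6.1 is to quantify motion-capture data, and Section 1.2 leaves perfecting the design to a later study. Component accuracy is a reasonable first step, and cumulative exposure is only one of four device aims in Section 1.2. This stands as a limit on severity: the gap is in the performance criteria and is not an error in a primary test. It does not remove the gap, because Section 6.3.1 sets explicit success marks that will support a feasibility claim.

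A reader might infer more than the documents support.

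- **That every stage has its own pass mark.** Only detection and biomechanical prediction do. The 14% figure therefore rests on an assumed mark for classification. Multiplying in 90% for phases, to say that only 0.95 x 0.95 x 0.90 = 81% of pitches come through correctly, has no basis in the plan: the 90% is a time-overlap rule for one movement segment.
- **That the device will under-read.** The 10% shortfall is a one-sided boundary case. The sign of the bias is open and 95% specificity permits false detections, for which the runs, swings and catches in Section 4.2.2 give ample opportunity.
- **That missed throws are known to be left out of the regression error.** Section 6.3.1 does not say whether the regression receives true segments or those the chain detected. Exclusion is a natural reading but an inference.
- **That nothing is checked end to end.** The Pilot Phase pitch count is a partial check, of count only.

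A practical objection also stands. Motion capture may not cover every game pitch. Section 1.1 places it during simulated play, Sections 3.1.3 and 4.2.2 can be read as attaching it to the movements performed afterwards, and Section 5.1.6 is ambiguous and gives a limited capture volume.

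**Conclusion.** The point holds as a gap in the analysis plan that should be closed before the data are analysed. Performance is scored by component, two of the four components have a success mark, and no analysis scores the load output of the full chain.

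Meeting both marks leaves the session workload error unbounded by the plan. At the limits it can be about 10% too low, using the plan's own figures with bias at -5% and no false detections. It can be about 14% too low if classification is also assumed to be 95% correct. Under other assumptions about the bias and false detections it is near zero or more than 10% too high. These figures show what is compatible with success and do not predict how the device will perform. The direction of any error cannot be known from the documents, which is the reason to measure it.

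**What to change.** Add to Section 6.3.1, in words such as these:

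> For each held-out Phase 1 child, the raw sensor recording will be run through the complete chain as on the device. The throw count will be compared with reviewed video, and the summed load with motion capture over all movements that have a motion-capture reference. Missed throws count as zero load, and load from false detections is added. The percentage error in each total will be reported per child, with its mean and SD. The statement on workload feasibility will rest on these results. Stage-wise results will be reported as diagnostics.

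The section should also say whether the stage-wise regression error uses true or chain-detected segments.

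If the sponsor wants a pass mark for the session total, it should be set and justified in advance. The 5% regression limit should not simply be carried over: a chain with exactly 95% sensitivity, no bias and no false detections already sits at -5%, so it would be a new and stricter requirement.

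The cost is one extra analysis with no added visits or participants. The load comparison is restricted to movements that were captured. The reported accuracy may look less favourable than the stage-wise figures.

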4.2.2 Phase 1 Study Visit

At the Epic Sports Biomechanics research facility, subjects will be asked to do the following activities:

- Height and weight measurements
- Physical Exam
- Wear the prototype device and participate in a simulated game
 - Pitch approximately 30-45 times using varying pitch types (fastball, change-up, etc.)
- Complete additional baseball-related movements with full the Epic Sports Biomechanics research facility monitors in a random order, including
 - Field-based overhand throws
 - Runs

- Bat swings
- Catching balls
- Return throwing device at end of session or earlier if requested by study team

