5.2 Efficacy Evaluations

5.2.1 Diagnostic Tests, Scales, Measures, etc.

Movement Data Processing: The first step in the processing chain is to apply calibrations and filters to correct intrinsic errors (e.g. sensor bias, scale factor, non-linearity) and extrinsic errors (e.g. sensor mounting, movement artifacts, external magnetic fields). This will be done using an Error-State Extended Kalman Filter (EKF) fusing the accelerometer, gyroscope, magnetometer, and a physical motion model together in a statistically valid fashion. Anomalous movements well outside of the expected range (e.g. a player bumping the sensor) are flagged by the sensor to avoid corrupting data interpretation. The filtered sensor data is then used to estimate time-series quantities such as short-time window 3-D motion paths, orientation stability, velocity vectors, and tangential and centripetal accelerations.

Movement Classification: The system is only interested in analyzing a subset of the movements executed during play hence the next step in the processing chain is detection / classification of movements of interest. This process begins with separation of processed time-series data into portions containing movements of unknown type. This is done with a classifier trained to discriminate fixed sized windows into either start of movement, end of movement, or other classes. This separation process is important as different actions will on average take differing amounts of time. Attempting to classify actions directly with fixed window sizes results in diminished discriminative power as the timeseries values used to produce these features will likely be taken from a period where the system is in multiple states [39], [40]. After action segmentation, a secondary feature set will be calculated over the movement timeseries and used to classify the movement to a known class of actions in the given sport (e.g. forehand swing, backhand swing, serve in tennis). IDL has had success with the decision tree classifier in previous efforts and will begin our research efforts with this algorithm. The tree is trained offline using the C4.5 algorithm with data acquired in the research facility [41]. The resulting decision trees are then used for real-time classification on the sensor hardware.

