6.3.2 Efficacy Analysis

Data recorded from the motion capture system will be analyzed with C-Motion Research Visual 3D v5 Professional and used to derive biomechanical variables of interest when performing movements associated with overuse injuries or of interest for performance monitoring. Analysis will calculate a time series of torques, compression forces, and tension forces on joints, ligaments, and muscles of interest. A biomechanist at the Epic Sports Biomechanics research facility familiar with baseball will review video of each movements of interest (e.g. pitches) and segment movements into their constituent phases. Additionally, the biomechanist will flag any abnormalities in data such as aborted movements and instances of improper form or technique.

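### The rule for a correct movement segment in 6.3.1 tests coverage only, and whether the 95% limits restrain over-long segments depends on a unit that is not stated

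*Combined protocol and SAP*

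**What the plan says.** Two adjoining sentences in section 6.3.1 (Baseline Data) of the combined protocol and SAP set the criteria. The first is applied to a segment: "Movement segment detection will be considered correct if the algorithm identifies 90% of time occupied by the movement". The second is applied to the algorithm: "Detection algorithms will be considered successful if they are able to operate with specificity and sensitivity of 95" (per cent). Neither sentence says whether sensitivity and specificity are counted per window, per unit of time or per movement, nor which activity forms the negatives.

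Section 5.2.1 describes how segments arise. The recording is first split by "a classifier trained to discriminate fixed sized windows into either start of movement, end of movement, or other classes". After that split, "a secondary feature set will be calculated over the movement timeseries and used to classify the movement". The reason given for segmenting first is that features from fixed windows "will likely be taken from a period where the system is in multiple states", which weakens discrimination. Phase segmentation is a later step: "After detection and classification, movements are further segmented into constituent phases".

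The reference labelling is in section 6.3.2, where a biomechanist "will review video of each movements of interest (e.g. pitches) and segment movements into their constituent phases". No boundary tolerance or overlap rule is attached to it.

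**The concern.** The denominator of the 90% rule is the true duration of the movement. Detected time that falls outside the movement does not enter the score, so starting too early or ending too late is never penalised. Nor does the rule require a detected segment to belong to a single movement, so a segment that runs from one movement into the next can be a hit for both.

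This matters because the next stage computes its classification features over the segment. Section 5.2.1 justifies segmentation by the need to avoid mixing several states in one feature window. An over-long segment brings that mixing back, and the segmentation step is still recorded as correct. What is at stake is the meaning of the reported segmentation accuracy, which is one of the feasibility results of the study.

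**Working it through.** The documents give no derived figure to reproduce here; 90% and 95% are set thresholds. The inputs are those two thresholds (6.3.1) and the window scheme (5.2.1). One further quantity, the share *f* of the recording occupied by movements, is not in the documents and is shown as a range.

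**Step 1. Coverage rule alone.** Let *r* be detected length divided by true length, for a segment that contains the whole movement. Coverage is 100% for every *r* of 1 or more, so the segment is always correct. The share of the segment outside the movement is (*r* − 1)/*r*.

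- *r* = 1.5: 0.5/1.5 = 33% outside
- *r* = 2: 1/2 = 50% outside
- *r* = 10: 9/10 = 90% outside

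**Step 2. Two movements in one segment.** Take two movements of length *L* separated by a gap *g*, and one segment of length 2*L* + *g*. It covers 100% of each movement, so both are scored correct whatever the gap. Relative to either movement, the share outside is (*L* + *g*)/(2*L* + *g*), which is never below 50%.

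**Step 3. What the 95% limits add, by unit.**

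(a) *Per movement.* Excess length within a segment already scored correct is not counted. There is no limit on length.

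(b) *On time.* Specificity of 95% allows false time of 0.05(1 − *f*) of the recording. In the worst case all of it is attached to true movements that are fully covered. Total detected time over total true time is then

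*r* = 1 + 0.05(1 − *f*)/*f*

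| *f* (assumed) | mean *r* | share outside |
|---|---|---|
| 50% | 1 + 0.05 × 0.50/0.50 = 1.05 | 4.8% |
| 20% | 1 + 0.05 × 0.80/0.20 = 1.20 | 16.7% |
| 10% | 1 + 0.05 × 0.90/0.10 = 1.45 | 31.0% |

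An average of at most 10% outside means *r* ≤ 1/0.9 = 1.111. That requires 0.05(1 − *f*)/*f* ≤ 0.111, or *f* of at least 31%. Even then the bound is on the mean, and single segments may be much longer.

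(c) *On start and end windows.* A late end is a missed end window plus a false one, so sensitivity now bites. *N* movements have 2*N* boundaries, and 95% sensitivity allows 0.05 × 2*N* = 0.10*N* misses. If each falls on a different movement, at most about 10% of all scored movements have a missed boundary. This limits how many segments are wrong, but not by how much, and it needs a matching tolerance that the plan does not give.

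**The case against.** The strongest reply is that the coverage sentence does not stand alone. A one-sided definition of a hit, paired with a specificity limit, is a normal construction, and the only detection unit that the documents describe is the start/end/other window. If that is the scoring unit, most of the gap closes. This stands as a limit on the point. But section 5.2.1 describes how the classifier works and does not say how it is scored, and the correct/incorrect label of a segment in 6.3.1 rests on the coverage sentence alone under any unit.

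A second reply is that a segment here means a phase. Phases adjoin, so a phase that runs long takes time from its neighbour, and a coverage rule applied to every phase would be largely two-sided. The wording favours whole movements: the rule refers to the time of the movement, and 6.3.1 lists phase segmentation as a separate item from movement detection.

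A third reply is that harm is not shown. That is right. Classification accuracy and biomechanical prediction error are quantified separately, so boundaries poor enough to matter may partly show up there.

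Three stronger inferences should be resisted:

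- A reader might conclude that the plan as a whole accepts segments of any length. That follows only if the 95% limits are counted per movement.
- A reader might take the values in the time-based table as likely. They are worst cases at assumed values of *f*.
- A reader might turn the 10% in (c) into a number of pitches per subject, because section 4.2.2 has each Phase 1 subject "Pitch approximately 30-45 times using varying pitch types". Nothing applies the 95% limit per subject. With the 10 evaluable subjects of section 3.1, the pooled pitches alone number about 300 to 450 (10 × 30 to 10 × 45), before throws, runs, swings and catches.

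**Conclusion.** The point holds in a conditional form. The per-segment rule is one-sided as written: a segment that contains the movement is correct at any length, and a merged segment can be correct for two movements. Whether the algorithm-level limits make up for this cannot be settled from the documents. The answer runs from no limit on length (per movement), through a limit on the mean that is loose when *f* is small (on time), to a limit that closes most of the gap (start and end windows).

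This rests on reading the 90% rule as applying to whole movements. The time-based figures rest further on the assumed *f*, full coverage, and all false time being attached to movements.

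The effect is minor. The study is exploratory, the primary endpoint in 6.1 does not depend on this rule, and no loss in later steps is demonstrated or claimed. The consequence is that the reported segmentation accuracy could look better than the boundaries are, and that two analysts could score the same output differently.

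**What to change.** In section 6.3.1, score a segment as correct only if it covers at least 90% of the reference movement and no more than a pre-set share of the detected segment lies outside it, with each detected segment matched to one reference movement. A share of 10% would mirror the 90% rule: a fully covering segment could then be at most 1/0.9 = 1.11 times the true length. The 10% is a choice, and the team may fix another value before analysis. An equivalent is to score the start and end boundaries within a pre-set tolerance.

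Alongside this, state the unit for sensitivity and specificity (start/end window, time or movement) and which activity forms the negatives. If start and end windows are meant, give the matching tolerance.

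The cost is a slightly stricter bar for segmentation and a little more analysis work. No new data are needed in principle, because the 90% rule already requires reference start and end times. For Phase 1 movements that the biomechanist labels on video, these are the outer edges of the labelled phases (6.3.2).
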